7 FDA IDE-RELATED DEVICE PREPARATION AND ADMINISTRATION PROCEDURES

Study-related device packaging will not be altered with respect to the device manufacturer's clinical supply packaging. However, the following label will be added to the devices described within the FDA IDE protocol associated with this clinical trial:

```
*** CAUTION ***
```

Limited to Investigational Use by Federal Laws and Regulations

7.1 Receipt of FDA IDE-related Devices

A representative from Abbott will ship the devices to Mayo Clinic and they will be properly inventoried prior to the scheduled date of surgical implantation. The representative will also train study personnel on how to use the clinician programmer during non-testing rehabilitation sessions.

The Nomad neurostimulation system will be purchased from Ripple Neuro, shipped to Mayo Clinic, and inventoried within the ART Lab.

Any product discrepancies or damage will be documented in the study files and the supplier will be notified. Then, appropriate action will be taken by the PI to fully address the issue.

7.2 FDA IDE-related Device Storage

ES electrode leads and the clinician programmer will be supplied directly by the Abbott distribution representative and/or stored in the ART Lab, which is a secured area that can only be accessed by ART Lab staff.

The Nomad system will be stored in the ART Lab.

7.3 Distribution of FDA IDE-related Devices

In accordance with Mayo Clinic policy, the brand, model, date of implantation, and date of explantation of all ES electrode leads will be recorded in the Surgical Inventory Management System. This information will be made available within the electronic medical record of each participant. Additionally, a copy of this information will be stored within each participant's case file.

7.4 Return or Destruction of FDA IDE-related Devices

Each month, as well as upon receipt of new or repaired devices, and at the completion of the study, there will be a reconciliation of devices shipped, devices utilized, and devices remaining. This reconciliation will be logged, signed, and dated within the Device Accountability Form. Any discrepancies noted will be documented and an investigation will be conducted to determine the cause of the discrepancy.

8 STATISTICAL DESIGN AND POWER

8.1 Sample Size Determination

Due to the pilot phase of this clinical trial, no formal power calculations were performed for this study. The number of subjects was selected based on budgetary, space, and personnel time constraints. Eight subjects will be enrolled to complete the activities of this clinical trial, depending on need for contingency subjects. All subjects will receive either 1 month of TS and rehabilitation or 1 month of ES and rehabilitation. Following either intervention, all subjects will be followed for follow-up assessments at 2 time points during 4 additional months.

8.2 Statistical Methods

Descriptive Statistics and Graphics

Continuous data will be summarized as median (inner quartile range). Categorical data will be presented as frequency (percentage). Graphical presentations of data will be used for all endpoints. Individual data points will be plotted over time, with distinctions made between data from TS and ES groups. Additionally, associations between measurements prior to and following ES intervention will be assessed using bivariate scatterplots. These associations will be summarized numerically with Spearman's correlation coefficient.

Modeling

The overall ES effect will be assessed by comparing models with and without the treatment indicators. Additionally, measurements taken under various conditions can be modeled simultaneously with appropriate effects for the different conditions. For example, SSEPs will be measured at the tibial and median nerves, each at 2 intensities. Effects for the different locations and intensities will be added to the model, along with effects for the 2 nerves as random effect nested within subject. Models will also be used to quantify associations between assessments at baseline and during the first month, with assessments at the end of the study. This may be used to determine whether there may be markers available to predict which subjects may respond to treatment.

Handling of Missing Data

Mixed modeling will not require complete data collection to conduct the analysis. Other analysis, such as bivariate analyses, which require complete data will be, conducted primarily using complete cases analysis. Sensitivity analyses will be conducted by imputing missing data with predictions from regression models based on baseline data.

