Objectives	 a. Identify relationships between stimulation inputs delivered to lumbosacral spinal circuitry and the corresponding electrophysiological outputs, during 4 weeks of motor training with stimulation, and over 16 weeks post-stimulation to determine residual effects, in individuals with SCI. b. Assess motor, sensory, and functional outcomes during 4 weeks of motor training with stimulation, and the retained effects over 16 weeks post-stimulation, in individuals with SCI. 							
Number of Subjects	8 subjects							
Diagnosis and Main Inclusion Criteria	American Spinal Injury Association Impairment Scale A-D							
Study Device	DS8R Isolated Biphasic Constant Current Electrical Stimulator (Digitimer Ltd) Abbott percutaneous trial lead for epidural neurostimulation (Model 3086) Ripple Nomad Neurostimulator							
Duration of Exposure	All subjects will complete either 1 month of transcutaneous spinal stimulation (TS) or temporary epidural spinal stimulation (ES) enabled rehabilitation sessions. Subjects will then be followed for an additional 4 months to complete follow-up assessments.							
Reference therapy	The reference therapy is clinical rehabilitation after SCI.							
Statistical Methodology	Descriptive statistics will be used to describe stimulation-related outcomes for each intervention. Repeated measures analyses of variance will be used to detect changes in outcomes over the course of rehabilitation.							

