This study will include adult humans that sustained a traumatic SCI at least one year before trial enrollment. To qualify for this study, SCI severity must be previously diagnosed with an AIS classified injury. One participant will be enrolled from each AIS classification (A, B, C, and D) for each intervention. All injuries must be located at or above the tenth thoracic vertebrae. Detailed inclusion and exclusion criteria are provided within the appropriate section of this protocol.

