2.1 Primary Objective

The primary outcome data collected will be used to compare spinal sensorimotor activity in muscles below the level of injury during TS or ES-enabled motor tasks in persons with chronic motor complete paralysis of the lower extremities due to traumatic SCI.

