3 STUDY DESIGN

3.1 General Design

This is a pilot study that will include a total of 8 subjects with chronic, motor complete or incomplete paralysis below the level of SCI. All subjects will complete either 1 month of TS or ES driven physical rehabilitation sessions (**Table 1**). All subjects will then be followed for an additional 4 months for follow-up assessments. Expected duration of subject participation is less than 6 months.

Table 1: Study Design

	PRE-INTERVENTION	INTERVENTION	POST-INTERVENTION	Follow-Up					
Subjects	Baseline Assessments	Minimum 12 Sessions	ents	Assessments					
50% of Sub	Clinical, Electrophysiology, Kinematic Assessments & Surveys	Stimulation + Motor Training	Training Kinematic Assessments						
	Tr	Kinematic	Kinematic veys	END					
	DDE INTERVENTION					∠			
	PRE-INTERVENTION	INTERVENTION	POST-INTERVENTION	Sul	ogy, Sur				
jects	Baseline Assessments	Minimum 12 Sessions		nysiology, & Sul	nysiology, & Sur	STUDY			
50% of Subjects		Minimum 12 Sessions Stimulation + Motor		Electrophysiolc &	Electrophysiolo &	STUD			
₽	Baseline Assessments Clinical, Electrophysiology, Kinematic Assessments & Surveys	Minimum 12 Sessions Stimulation + Motor	End Assessments Clinical, Electrophysiology, Kinematic Assessments & Surveys	Clinical, Electrophysiology, & Su	Clinical, Electrophysiology, & Sur	STUD			

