4.1 Inclusion Criteria

- Spinal cord injury due to trauma located at or above the tenth thoracic vertebrae (T10)
- American Spinal Injury Association grading scale of A-D (2 from each) below the level of SCI
- Intact spinal reflexes below the level of SCI
- At least 1-year post-SCI
- At least 22 years of age
- Willing to use medically acceptable methods of contraception, if female and of childbearing potential

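### Section 8.2's only treatment test leaves out own baseline and AIS grade, does not define its treatment indicators, and is labelled an ES effect although an arm term estimates ES minus TS

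*Combined protocol and SAP*

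**What the plan says.** The treatment comparison rests on one sentence in Section 8.2 (Modeling): "The overall ES effect will be assessed by comparing models with and without the treatment indicators". The section does not say whether the indicators denote arm, arm by time, before/after, or stimulation on/off, and it gives no test statistic or reference distribution. Baseline appears in 8.2 only for predicting response and for imputing missing values. AIS grade does not appear. The model has a subject level, as shown by the SSEP example with "effects for the 2 nerves as random effect nested within subject".

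Other statements do not settle the form of the test:
- The Study Summary says "Repeated measures analyses of variance will be used to detect changes in outcomes over the course of rehabilitation" and names no arm term.
- The descriptive part of 8.2 says "associations between measurements prior to and following ES intervention will be assessed using bivariate scatterplots", which covers one arm only.

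The design makes grade a matching factor. Section 1.1 says "One participant will be enrolled from each AIS classification (A, B, C, and D) for each intervention", and Section 4.1 lists "American Spinal Injury Association grading scale of A-D (2 from each) below the level of SCI". Under Section 5.2, subjects enter an arm by availability, or by their own choice when both arms are open. Under Section 8.1, everyone receives one month of TS or ES together with rehabilitation.

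The primary objective (2.1) concerns "TS or ES-enabled motor tasks in persons with chronic motor complete paralysis of the lower extremities due to traumatic SCI", while Section 3.1 enrols "8 subjects with chronic, motor complete or incomplete paralysis below the level of SCI".

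**The concern.** There are two problems. First, the planned comparison ignores the factor on which the arms are matched and the measurement most likely to absorb differences between subjects. With at most eight subjects, this choice can dominate the width of the interval. If the matching fails, it also affects where the estimate is centred.

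Second, the label promises something the design does not deliver. No arm receives rehabilitation alone, although the Study Summary names clinical rehabilitation as the reference therapy.

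The reported ES-TS result would therefore depend on a model form chosen after the data are in. A needlessly wide interval could be read as no difference between the techniques, and an ES-minus-TS estimate could be read as the effect of ES.

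**Working it through.** **What each indicator would estimate**
- Arm: ES minus TS, because both arms receive stimulation and training (8.1).
- Before/after within ES: stimulation mixed with training and time.
- Stimulation on/off within ES subjects: an acute effect, for outcomes recorded both ways. Section 6.6.1 allows this for kinematics, EMG and foot pressure; Section 6.6.2 plans it for urodynamics.

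None of these isolates ES plus training.

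**Inputs.** From the documents: 4 v 4, one subject per AIS grade per arm. Section 8.1 reports no power calculation, so there is no plan figure to reproduce. Assumed: two-sided 5%, within-grade SD 1, and a grade share s of variance of 0, 50% or 80%. Grade variance is then s/(1-s) and total SD is 1/√(1-s).

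**Mechanism.** The true variance of the arm difference is 1/4 + 1/4 = 1/2. The unadjusted analysis estimates it as s²/2, where the pooled variance s² has expectation 1 + (4/3) × grade variance.
- s = 50%: 1 + 1.333 = 2.333, so the standard error is about √2.333 = 1.53 times too large.
- s = 80%: 1 + 5.333 = 6.333, so about 2.52 times too large.

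A subject random effect does not help. Grade is a between-subject difference, and between-subject variance is the error term for arm.

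**Half-widths.** Simulation of 300,000 trials per setting gives mean 95% half-widths in total SD. The s = 0 values follow directly: unadjusted 2.447 × 0.959 × 0.707 = 1.66 (6 df); matched pairs 25% wider, 1.66 × 1.25 = 2.07 (3 df).

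| Analysis | s = 0 | 50% | 80% |
|---|---|---|---|
| Unadjusted, size of 5% t test | 5% | 0.5% | <0.01% |
| Unadjusted, half-width | 1.66 | 1.82 | 1.92 |
| Linear AIS score, grades equally spaced | 1.73 | 1.22 | 0.77 |
| Linear AIS score, only grade D differs | 1.73 | 1.58 | 1.50 |
| Matched pairs (2.07 × √(1-s)) | 2.07 | 1.46 | 0.93 |

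If only grade D differs, the linear score is itself conservative: size 1.9% at 50% and 0.1% at 80%. Matched pairs keep 5% throughout, but narrow the interval only above a grade share of about 29%.

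**Likelihood-ratio reference.** For the same contrast LR = 8 ln(1 + t²/6). Rejecting above 3.841 means t² > 6(e^0.480 - 1) = 3.70, or |t| > 1.92, against 2.447 for the t test. The resulting size is 10.3% at s = 0, 6.6% at 20% and 3.2% at 40%.

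**Arm-by-time.** With four visits, subject SD 1 and within-subject SD 0.5, the change contrast has size 5% if the grade effect is constant over time. If grade also shifts the change by 0.5 or 1.0 subject SD per SD of grade score, size falls to 0.9% or 0.01%.

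**Broken matching.** Suppose the ES arm loses its grade D subject. With standardised grade scores ±1.342 and ±0.447, the remaining mean is (-1.342 - 0.447 + 0.447)/3 = -0.447. The unadjusted contrast is then biased by √s × (-0.447): -0.32 total SD at 50% and -0.40 at 80%. The linear score removes this if grades are equally spaced. If only D differs it leaves 4/7 of an unadjusted bias of -0.41 or -0.52, that is -0.23 or -0.30.

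**The case against.** This is a pilot. Section 3.2 declines to designate formal endpoints, Section 8.1 disclaims power, no significance level is stated, and 8.2 plots individual data by arm. That stands, so size serves here only as a measure of interval calibration. It does not remove the point, because 8.2 still commits to a model-based effect assessment and 2.1 makes TS versus ES the primary comparison.

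Several stronger readings are tempting but unsupported:
- **The test is conservative whatever is done.** The plan gives no reference distribution. Under a chi-square likelihood-ratio test the error goes the other way when grade is weak.
- **No indicator could yield any ES effect.** The on/off recordings could give an acute one for some outcomes.
- **Adjustment narrows the interval 2.5-fold.** That is 1.92/0.77, and it needs an 80% share and linear grade effects. If only D differs the ratio is 1.92/1.50 = 1.28. At share 0 adjustment widens the interval.
- **Arm-by-time solves the problem.** It does so only if grade does not predict change.
- **Matching will be lost.** Section 4.4.1 allows replacement within the cohort without restating the grade quota, but the quota in 1.1 and 4.1 may still apply. Section 8.3 lets the investigator keep subjects who completed most visits. The bias is conditional.
- **The primary comparison is 2 v 2.** Section 2.1 says motor complete, but no such subset analysis is planned and the other sections include incomplete injuries. This is wording to reconcile.

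Results for arm effects pooled over follow-up depend on how much of the difference persists after stimulation ends. The trial is meant to find that out, so I do not rely on them.

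**Conclusion.** The concern holds in a limited form. The only treatment test in 8.2 omits own baseline and AIS grade, does not define its indicators, and carries a label that the design cannot support.

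On a t or F reference with matching intact, an unadjusted arm contrast is unbiased by grade but increasingly conservative as grade becomes prognostic. A 50% share inflates the half-width from 1.22 to 1.82 total SD if grade effects are linear, and from 1.58 to 1.82 if only D differs. On a chi-square likelihood-ratio reference it is anti-conservative for weak grade effects. Bias from grade enters only if matching breaks. Bias from self-selected arms is possible either way.

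All grade shares and variance components are assumptions, since the documents give none. What the change would improve is the estimate, its interval and its label.

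**What to change.** 1. Replace the *overall ES effect* label with *ES-versus-TS difference*. Define the treatment indicator as arm, with arm-by-visit. Report any stimulation on/off contrast separately, as an acute within-subject effect.
2. For outcomes with a pre-intervention value, model the post-baseline visits with own baseline, visit, arm, arm-by-visit and a subject random effect. Use a small-sample reference such as Kenward-Roger, not a chi-square likelihood-ratio test. State that baseline adjustment reduces, but may not remove, bias from non-random allocation. This model has no AIS term, so it can remain conservative if grade predicts change beyond baseline.
3. For outcomes without a pre-intervention value, adjust for AIS grade as a linear score. Show the matched-pair (grade-block) analysis and the within-grade ES-TS differences alongside, because the score does poorly when grade effects are not linear.
4. Reconcile the motor-complete wording of Section 2.1 with the A-D population in Sections 1.1, 3.1 and 4.1.

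The change is to analysis wording and needs no new data. It costs about one residual degree of freedom. If the covariate is uninformative, the interval is about 4% wider with the AIS score (1.73/1.66) or about 15% wider with own baseline. Four grade blocks would cost three degrees of freedom and 25%, so they belong beside the main analysis, not in its place.

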5.2 Method for Assigning Subjects to Treatment Groups

Four subjects will be assigned to each treatment arm based on availability at the time the subject volunteers to participate (Total subjects studied: 8). If both arms are enrolling in

parallel at the time a subject volunteers to participate, he/she will be allowed to choose the treatment arm in which to enroll.

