6.3 Period of Follow-up after TS

After 1 month of TS and motor training, each subject will be asked to complete two follow-up assessments at time points 1 month and 4 months after completing the intervention to monitor changes in primary and secondary outcome measures. Subjects will be asked to refrain from partaking in additional therapies or interventions with the goal of improving functional measures related to their SCI during this 4-month follow-up period.

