Somatosensory evoked potentials (SSEPs): SSEPs will be recorded through surface electrodes to measure conduction in the peripheral nerves, cervical and lumbosacral spinal cord, deep brain structures, and sensory cortex. Skin will be cleaned with alcohol and prepared using mild abrasive tape for placement of surface electrodes. For tibial recordings the tibial nerve will be stimulated behind the medial malleolus with recordings on the scalp utilizing a Fz,-CZ montage (International 10-20 System for EEG electrode placement), the cervical spine (C5 reference to Fz), the L1 spine (referenced to iliac crest), and the popliteal region. For median SSEPs, the median nerve will be stimulated at the wrist with recording electrodes at the scalp (C3-C4), the cervical spine (C5-Fz), Erb's point (referenced to contralateral Erb's) and the elbow. Repeated single-pulse electrical stimulation will be delivered at intensities of 1-1.5 times motor threshold for visual twitch for each of the four nerves evaluated. Averaged responses for up to 256 stimuli will be recorded for each of these two intensities for the right and left median and tibial nerves. Simultaneous bilateral stimulation will be applied if no recognizable responses are recorded from the scalp leads. Stimulation delivery rates will not exceed 2 per second. Recorded data will include amplitudes, peak latencies and interpeak latencies. Existing SSEPs within 6 months of screening may be acceptable for Baseline results at the investigators' discretion.

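### The worked SSEP model in 8.2 has no subject-by-visit term and no side of nerve, so tests of change over time use the wrong error term

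*Combined protocol and SAP*

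**What the plan says.** Section 8.2 (Modeling) offers SSEPs as its worked example of modelling several conditions at once. It describes the data as "SSEPs will be measured at the tibial and median nerves, each at 2 intensities". For fixed effects it says "Effects for the different locations and intensities will be added to the model", and for the random part it gives "effects for the 2 nerves as random effect nested within subject". No term for visit within subject and no term for side of the body is named.

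Section 6.6.1 (Electrophysiology tests, SSEPs) describes more recordings than that. Intensity is set relative to motor threshold "for each of the four nerves evaluated", and averaged responses are taken "for each of these two intensities for the right and left median and tibial nerves".

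Table 3 schedules SSEPs before the intervention, after it, and at follow-up. Sections 6.3 and 6.5 define follow-up as "two follow-up assessments at time points 1 month and 4 months after completing the intervention", so there are four SSEP visits.

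The Study Summary gives another method for change over time: "Repeated measures analyses of variance will be used to detect changes in outcomes over the course of rehabilitation". Section 8.2 does not mention it.

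**The concern.** Change during training and its retention afterwards are the stated objectives, and Table 3 lists SSEPs among the primary outcomes. A test of change needs an error term that reflects how much a subject's readings move from one visit to the next for no reason of interest.

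Some of that movement may be common to all of a subject's recordings on a day. Skin preparation and electrode placement are repeated each time. Section 6.6.1 also lets an SSEP study up to six months old serve as baseline, so the whole baseline set may come from a different session from the later ones. With only subject and nerve-within-subject as random effects, a common shift of this kind is spread into the residual as if it were separate noise in each recording. The standard error of a visit contrast, or of an arm-by-visit contrast, is then too small.

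The missing side term is a separate defect and works the other way. Stable left-right differences within a nerve type also fall into the residual. They cancel out of a visit contrast, so they make its standard error too large.

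**Working it through.** The plan states no alpha, SSEP variance or effect size, so there is no planned figure to reproduce. The check asks what a test of no change would do under the stated random structure.

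**Inputs from the documents**
- 8 subjects, 4 per arm (5.2, 8.1).
- Recordings per visit for a given measure: 2 nerve types × 2 sides × 2 intensities = 8 (6.6.1).
- Random structure: subject, and 2 nerves within subject (8.2).

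**Assumptions**
- Two-sided 5% test; visit added as a fixed effect; a subject intercept fitted.
- Within-subject variance, excluding stable nerve and side differences, scaled to 1. A share ρ of it is a visit effect and 1 − ρ is recording-level noise.
- Stable left-right differences have SD s, taken as 0 or 0.7.

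**Pre-to-post contrast, 2 visits (128 values)**

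Residual df under the 8.2 structure: 128 − 1 (mean) − 3 (visit, nerve type, intensity) − 7 (subject) − 7 (nerve within subject) = 110. The critical t is 1.98.

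Case 1, visit effect common to all eight recordings:
- True variance of the contrast = 2 × [ρ/8 + (1 − ρ)/64].
- Expected residual mean square = (1 − ρ) + ρ × (7 × 8)/110 + s² × (16 × 4)/110. Here 7 df of subject-by-visit each carry 8ρ, and 16 df of side within nerve each carry 4s².
- Model standard error = √(2 × residual mean square/64).

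With ρ = 0.10 and s = 0:
- True SE = √{2 × (0.0125 + 0.01406)} = 0.230.
- Residual mean square = 0.9 + 0.051 = 0.951, so model SE = 0.172.
- The test rejects when |z| exceeds about 1.98 × 0.172/0.230 = 1.48, a probability of about 14%.

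At ρ = 0.20 and 0.30 the true SE is 0.274 and 0.311, against a model SE of 0.168 and 0.163.

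Case 2, visit effect specific to each limb and nerve (shared by two recordings):
- True variance = 2 × [ρ/32 + (1 − ρ)/64].
- The visit part of the residual mean square becomes ρ × (47 × 2)/110.

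Simulated false-positive rates agree with these formulas to within about a percentage point:

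| Visit variation | Side SD | ρ = 0 | 0.10 | 0.20 | 0.30 |
|---|---|---|---|---|---|
| Common to all 8 | 0 | 5% | 13-14% | 22-23% | 30% |
| Common to all 8 | 0.7 | 2.6% | 9-10% | 16-17% | 24% |
| Limb-specific | 0 | 5% | 6-7% | 7-8% | 9-10% |
| Limb-specific | 0.7 | 2.6-2.8% | 3.5% | 4.6% | 5.7% |
| One value per subject per visit, 7 df | either | 5% | 5% | 5% | 5% |

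**All four visits (3-df visit test, common visit effect)**
- No side variance: 12.5%, 21.6% and 51.8% at ρ = 0.05, 0.10 and 0.30.
- Side variance equal to the residual: 0.9%, 8.3% and 36.2% at ρ = 0, 0.10 and 0.30.
- Arm-by-visit is nearly identical (21.6% at ρ = 0.10 with no side variance).
- Replacing two nerves by four, still without a subject-by-visit term: 21.2-21.5% at ρ = 0.10.
- Testing against subject-by-visit (18 df): 4.8-5.4% in every setting.
- Arm main effect tested over subjects: 4.6-5.4% throughout.

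**The case against.** The case for leaving 8.2 alone is substantial.

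- **The model is illustrative.** It is introduced as an example of what can be done, the base model is not written out in full, and no visit contrast is listed for it. This stands and lowers the severity. It remains the only concrete random structure in the plan, so it is the natural template for the analyst.
- **Repeated measures ANOVA would normally use the right error term.** It tests time against subject-by-time. This also stands, but 8.2 never mentions that method and its missing-data text relies on mixed modelling. The plan holds two methods with different error terms and does not choose between them.
- **The visit effect may not be common to all eight recordings.** Threshold is set nerve by nerve, stimulation sites differ, and most recording sites differ between median and tibial studies. If visit variation is mainly limb-specific, the error is small, as the third and fourth rows of the table show. Nothing in the documents says where between the extremes the truth lies.
- **Eight responses are not assured.** Bilateral stimulation replaces separate sides when no scalp response is recognised.
- **The two nerves might mean left and right**, since location is already a fixed effect. On that reading the text is ambiguous and still needs reconciling with 6.6.1.

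A reader might infer that counting four nerves as two causes false positives. It does the reverse for visit tests. A reader might also infer that the model treats 64 values per visit as independent (8 subjects × 8 recordings). It does not: the recordings are independent only given their subject and nerve effects.

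**Conclusion.** The omission is real. As written, the SSEP model has no visit-level term and no side term, does not match the four nerves recorded, and sits beside a different method in the Study Summary. Tests of visit change and arm-by-visit would therefore have the wrong error term.

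The size is conditional. For a pre-to-post test at a nominal 5%, the false-positive rate is about 13-30% with a common day effect of 10-30%, about 10-24% with side SD 0.7 added, about 4-9% if visit variation is limb-specific, and about 2.6% with left-right differences and no visit effect. All of these rest on assumed variances. The documents do not support a statement that the trial will declare changes far too often, because even the net direction is unknown.

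The point does not reach an arm main effect tested over subjects, provided a subject intercept is fitted. If the nested term were fitted without one, that test would reject about 9-14% of the time under the four-visit assumptions.

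The trial has eight subjects in non-randomised arms ("Four subjects will be assigned to each treatment arm based on availability at the time the subject volunteers to participate"), no power calculation, no stated alpha, and individual data plotted for every endpoint. In that setting this is a worthwhile correction, not a must-fix.

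**What to change.** In 8.2, do one of the following:
- specify random subject, nerve-side within subject (four levels) and subject-by-visit, with a small-sample degrees-of-freedom method; or
- average all of a subject's recordings for a given measure to one value per subject per visit, and test change on the 8 subjects with subject-level degrees of freedom.

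The subject-by-visit term is the essential part. Correcting the nerve count alone does not repair the visit test.

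Reconcile 8.2 with the four nerves in 6.6.1 and with the repeated measures ANOVA in the Study Summary, so that one method is named for change over time. If MEP or EMG recordings from several muscles or sites are modelled jointly, use the same visit-level error term there.

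The cost is about two sentences and no new data. Intervals will usually be wider. With no visit effect and no side differences, the subject-level pre-to-post test uses a critical t of 2.36 on 7 df instead of 1.98 on 110, so its interval is about 2.36/1.98 = 1.19 times as wide. Averaging also gives up comparisons between nerves, which the mixed model keeps.
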